#### **4.4.1.1.7 Ongoing**

Ongoing is derived from the last daily intensity of the solicited period computed as described in Section 4.4.1.1.1 and the maximum intensity on the ongoing period. The investigator's ongoing flag is not used because the measurement would determine the ongoing status of the reaction. Note the intensity could be considered None (not a reaction) in the analysis despite being considered a reaction by the investigator (e.g., swelling measurement  $> 0$  mm but  $< 25$  mm in adults). If the last daily intensity of the solicited period is at least Grade 1 and maximum intensity on the ongoing period is also at least Grade 1, then the reaction is considered ongoing. In any other cases the reaction will not be considered as ongoing.

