**Table 9.1: Solicited injection site reactions: terminology, definitions, and intensity scales**

CRF term (MedDRA lowest level term [LLT])	Injection site tenderness	Injection site erythema	Injection site swelling
Diary card term	Tenderness	Redness	Swelling
Definition		Presence of a redness including the approximate point of needle entry	Swelling at or near the injection site Swelling or edema is caused by a fluid infiltration in tissue or cavity and, depending on the space available for the fluid to disperse, swelling may be either soft (typically) or firm (less typical) to touch and thus can be best described by looking at the size of the swelling
Intensity scale*	Grade 1: Minor reaction when injection site is touched  Grade 2: Cries or protests when injection site is touched  Grade 3: Cries when injected limb is moved, or the movement of the injected limb is reduced	Grade 1: > 0 to < 25 mm  Grade 2: $\geq 25$ to < 50 mm  Grade 3: $\geq 50$ mm	Grade 1: > 0 to < 25 mm  Grade 2: $\geq 25$ to < 50 mm  Grade 3: $\geq 50$ mm

\* For the subjective reaction of tenderness, parents / guardians will record the intensity level (Grade 1, 2, or 3) in the diary card. For the measurable reactions of redness and swelling, they will record just the size of the reaction, and the classification as Grade 1, 2, or 3 will be assigned at the time of the statistical analysis.

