### 4.4 Derived Endpoints: Calculation Methods

#### 4.4.1 Safety

##### 4.4.1.1 Solicited Reactions

###### 4.4.1.1.1 Daily Intensity

All daily records for solicited reactions will be derived into daily intensity according to the following classification: None, Grade 1, Grade 2, Grade 3, or Missing.

For the derivation of daily intensities the following sequential steps will be applied:

- 1) Solicited reactions (except Fever) with an investigator presence recorded as “No” and with all daily records missing then all daily intensities will be derived as None.

- 2) For a temperature partially missing after decimal point, the data will be analyzed replacing “MD” (missing data) by zero. For example, a “39.MD” daily temperature will be considered as “39.0°C” at the time of analysis.
- 3) For non-measurable solicited reactions, daily intensities will correspond to daily records reported in the clinical database. For measurable solicited reactions the daily measurements reported in the clinical database will be converted based upon the intensity scales defined in the protocol; this assumes a reaction that is too large to measure (non measurable, “NM”) is Grade 3. Note the intensity could be considered “None” (not a reaction) in the analysis despite being considered a reaction by the investigator (e.g., swelling measurement  $> 0$  mm but  $< 25$  mm in adults).

Note: The maximum intensity on the ongoing period is derived from the record of the maximum intensity/measurement after the end of the solicited period following the rule described above.

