#### **4.4.1.1.6 Overall Number of Days of Occurrence**

If a reaction is ongoing at the end of the solicited period, then the overall number of days of occurrence is derived from the daily intensities and the stop date of the reaction after the end of the solicited period. The overall number of days of occurrence is:

- (stop date – last vaccination date) + (number of days of occurrence within the solicited period) – length of the solicited period + 1

If the stop date is missing or incomplete (contains MD), the overall number of days of occurrence will be considered as Missing.

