## 5.3 Handling of Missing Data and Outliers

### 5.3.1 Safety

No replacement will be done. In subject listings, partial and missing data will be clearly indicated as missing.

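### SAP 4.4.1.1.7 turns a missing D7 or post-D7 intensity into a definite not ongoing, even when the investigator's flag and a later stop date say otherwise

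*SAP*

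**What the plan says.** Under SAP 4.4.1.1.7, ongoing status comes from two derived intensities: the last daily value of the solicited period (D7) and the maximum after it. The first must be Grade 1 or higher, and if the "maximum intensity on the ongoing period is also at least Grade 1, then the reaction is considered ongoing". The rest is settled in one line: "In any other cases the reaction will not be considered as ongoing". The investigator's tick-box is set aside: "The investigator's ongoing flag is not used because the measurement would determine the ongoing status of the reaction".

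The inputs are defined in SAP 4.4.1.1.1: "All daily records for solicited reactions will be derived into daily intensity according to the following classification: None, Grade 1, Grade 2, Grade 3, or" a fifth class, Missing. The post-D7 input is a single record: "The maximum intensity on the ongoing period is derived from the record of the maximum intensity/measurement after the end of the solicited period". SAP 5.3.1 states the general policy on gaps in safety data: "No replacement will be done. In subject listings, partial and missing data will be clearly indicated as missing".

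Ongoing status then controls whether the stop date is used. SAP 4.4.1.1.6 reads: "If a reaction is ongoing at the end of the solicited period, then the overall number of days of occurrence is derived". Its inputs are the daily grades and the date on which the reaction stopped. If that date is missing or incomplete, the result is Missing. The section gives no value for a reaction that is not ongoing.

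**The concern.** The reason for setting the flag aside is that a measured value should take precedence over the investigator's opinion. That is sound when a value exists. A recorded temperature below 38.0°C is not fever under Protocol Table 9.2, whatever box was ticked. It gives no ground for setting the flag aside when the value is blank, yet the catch-all sentence treats a blank in the same way as an observed None.

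This also sits badly with neighbouring rules. Missing presence stays missing (SAP 4.4.1.1.3), and an ongoing reaction without a stop date gets a Missing duration (4.4.1.1.6). A reaction with a valid stop date but a blank D7 instead has that date ignored, so the case with more information on when the reaction ended gets the firmer and shorter answer.

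At stake are the ongoing classification and the overall number of days for reactions that outlast the diary week. Protocol 9.3.2.3.2 has solicited reactions followed until resolution, so information after D7 is collected in order to be used.

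**Working it through.** The documents give no duration figure to reproduce, so the check applies the SAP rules to worked cases.

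**Inputs**
- Solicited period D0 to D07 (Protocol 9.3.2.3.2), taken as 8 daily records. The SAP does not state the length as a number.
- Days within the period: the count of days graded 1 to 3 (SAP 4.4.1.1.5).
- Overall days if ongoing: (stop date - vaccination date) + days within the period - length + 1 (SAP 4.4.1.1.6).
- Overall days if not ongoing: not stated. The natural reading is the D0 to D7 count, and it is used below.

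**Check on a complete record.** A reaction from D0 to D10 lasts 11 days. The formula gives 10 + 8 - 8 + 1 = 11, which is correct. A length of 7 would give 12, so 8 is the length that fits.

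**Incomplete records, stop date known**

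| Reaction | True days | Complete record | D7 blank, SAP rule | Post-D7 blank, SAP rule |
|---|---|---|---|---|
| D0 to D10 | 11 | 10 + 8 - 8 + 1 = 11 | 7 | 8 |
| D5 to D12 | 8 | 12 + 3 - 8 + 1 = 8 | 2 | 3 |

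If the recorded stop date were used instead:
- D0 to D10: 10 + 7 - 8 + 1 = 10 with D7 blank, and 11 with the post-D7 intensity blank.
- D5 to D12: 12 + 2 - 8 + 1 = 7 with D7 blank, and 8 with the post-D7 intensity blank.

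**Example in the summary.** Grade 1 on D4, D5 and D6, D7 blank, flagged ongoing, post-D7 maximum 30 mm (Grade 2 in Protocol Table 9.1), stop date D10. As written, the reaction is not ongoing and counts 3 days. Treated as ongoing, it counts 10 + 3 - 8 + 1 = 6. If it was continuous from D4 to D10 it lasted 7 days. The remaining day is lost because 4.4.1.1.5 does not count an ungraded D7, and that loss is separate from the ongoing rule.

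**What does not change.** The D0 to D7 count is taken from the daily grades alone, so it is 3 in this example under either rule. An ongoing reaction with both intensities but no stop date is Missing, not shortened.

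**Size on average.** The documents give neither the share of reactions lasting beyond D7 nor the rate of blank intensities. As an assumption only, let 2% to 10% of reactions run from D0 to D10, and let 5% to 20% of those lack the post-D7 intensity. Each such record loses 11 - 8 = 3 days, so the mean falls by between 0.02 × 0.05 × 3 = 0.003 and 0.10 × 0.20 × 3 = 0.06 days. Longer persistence or more blanks would raise this.

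**The case against.** The strongest reply is that little depends on this rule. The protocol endpoint (9.3.2.2) is the number of days of occurrence for reactions up to 7 days after vaccination, and SAP 4.4.1.1.5 derives it without ongoing status. SAP Table 5.2 does list duration, but in rows that run to 7 days after D0. Gaps should also be few: the diary is reviewed with the parent at Visit 2 (Protocol 5.1.4), unclear entries are taken up at interview (11.1), and missing diary data are clarified verbally (13.2). All of this stands and limits the size of the problem. It does not justify treating the remaining blanks as evidence that a reaction ended.

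Three stronger readings are tempting, and the documents do not support them.
- A reader might infer that reactions lasting beyond D7 are cut off in general. They are not: with both intensities recorded, the full duration is kept.
- A reader might infer that the rule cannot work for the six of nine solicited reactions that are not measured (tenderness, vomiting, crying, drowsiness, appetite, irritability). The test is on intensity grade, and SAP 4.4.1.1.1 takes the recorded grade for these, so a recorded grade settles their status.
- A reader might take the adult swelling example (below 25 mm counted as none) as the grading used here. Protocol Table 9.1 grades any swelling above 0 mm as Grade 1, and the SAP grades by the protocol's scales, so the example has no operative effect.

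It is also fair to say that the 3-day result is a reading of a silence in 4.4.1.1.6, not a stated value.

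**Conclusion.** The point holds within narrow limits. For a record with a blank D7 or post-D7 intensity, the SAP assigns not ongoing and so disregards a flag and a valid stop date. Its stated reason does not reach that case. The consequences are confined to the ongoing classification and the overall number of days in 4.4.1.1.6. Where the classification is wrong, the error is always towards a shorter reaction. In the worked cases an affected record loses from 3 days (6 to 3) to 5 days (7 to 2, or 8 to 3), compared with using its stop date.

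These figures assume an 8-day solicited period and the D0 to D7 count as the default for reactions that are not ongoing. The number of affected records cannot be found in the documents. The average effect is probably small, and the safety objectives are observational with no hypothesis test, so no trial conclusion turns on it. It merits correction because it shortens safety durations in one direction and the data to avoid it are already recorded.

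**What to change.** In SAP 4.4.1.1.7, state three cases in order:
1. If both intensities are Grade 1 or higher, the reaction is ongoing.
2. If either intensity is recorded as None, it is not ongoing, whatever the flag says.
3. If neither is None and at least one is missing, a stop date after D7 or the investigator's ongoing flag decides. If that makes the reaction ongoing and there is no valid stop date, overall duration is Missing.

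The second case is needed. A simpler rule that let the flag decide whenever any value is missing would override observed data. Take fever on D1 and D2, D7 recorded as None, post-D7 intensity blank, and a flag with a stop date on D10. That rule would give 10 + 2 - 8 + 1 = 5 days despite a recorded normal D7.

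In SAP 4.4.1.1.6, state that overall days equal the D0 to D7 count when the reaction is not ongoing. List the records decided under the third case.

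The cost is a few sentences, a few lines of programming and slightly longer reported durations. No new data are needed. Removing the adult 25 mm example from 4.4.1.1.1, 4.4.1.1.7 and 4.4.1.2.2 would be an editorial tidy-up only.

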#### **4.4.1.2 Unsolicited Non-serious AEs**

##### **4.4.1.2.1 Presence**

An observation will be considered an event if it has at least a verbatim term and is not a Grade 0 intensity event. Grade 0 events should be included in the listing “Unsolicited non-serious adverse events not included in the safety analysis.”

##### **4.4.1.2.2 Intensity**

Intensity for unsolicited non-serious adverse event (AE) will be derived according to the following classification: None, Grade 1, Grade 2, Grade 3, or Missing.

If the unsolicited non-serious AE is measurable and its preferred term is part of the list of solicited reactions, then the measurement is derived based upon and following the same rule than the intensity scales defined in the protocol for that measurable injection site or systemic reaction. Note the intensity could be considered “None” (not a reaction) in the analysis despite being considered a reaction by the investigator (e.g., swelling measurement  $> 0$  mm but  $< 25$  mm in adults).

Intensity for the other unsolicited non-serious AEs will correspond to the value reported in the CRF.

The maximum intensity corresponds to the highest intensity for a unique term.

#### 4.4.1.2.3 Last Vaccination

Last vaccination before an unsolicited non-serious AE is derived from the visit numbers provided in the clinical database and is calculated as follows:

- If an unsolicited non-serious AE has a non-missing visit number, the visit number should be used to determine the last vaccination before the unsolicited non-serious AE

If the visit number is missing, then the start date should be used to determine the last vaccination before the unsolicited non-serious AE

#### 4.4.1.2.4 Time of Onset

Time of onset is derived from the start date of the unsolicited non-serious AE provided in the clinical database and the date of last vaccination:

- start date of the unsolicited non-serious AE – date of previous vaccination

The time of onset should be considered as missing only if one or both of the dates are missing or partially missing.

The unsolicited non-serious AEs will be analyzed “Within 30 days”, which corresponds to AEs with a time of onset between 0 and 30 days after vaccination or missing. An AE with missing time of onset will be considered to have occurred just after the vaccination indicated by the visit number, so will be included in these tables.

Note: Unsolicited non-serious AE that occurred before vaccination (negative time of onset) or with a time of onset higher than defined above will not be included in analysis, but will be listed separately.

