## 6.7 Concomitant Medications and Other Therapies

At the time of enrollment, ongoing medications including other therapies e.g., blood products, should be recorded in the source document as well as new medications prescribed for new medical conditions / AEs during trial participation.

Documentation in the CRF of concomitant medication will be limited to specific categories of medication of interest beginning on the day of vaccination. This may include medications of interest that were started prior to the day of vaccination.

Reportable medications will be collected in the CRF from the day of vaccination to the end of the solicited and unsolicited follow-up period (e.g., 30 day safety follow-up) as they may impact the response to the vaccination and impact the consistency of the information collected on concomitant medications at any vaccination.

The “reportable” medications are distributed according to 3 categories. These are:

- Category 1 antipyretics, analgesics, non-steroidal anti-inflammatory drugs (NSAIDs), corticosteroids, and other immune modulators.

*Note: inhaled and topical steroids should not be captured.*

- Category 2: Reportable medications used to define the Per-Protocol Analysis Set (PPAS). For example:
  - Influenza and other non-study vaccines: Influenza vaccine in the 2 weeks preceding the trial vaccination up to the subject’s termination from the trial and any other vaccines (other than the study vaccine) in the 4 weeks preceding the trial vaccination up to the subject’s termination from the trial
  - Immune globulins, blood or blood-derived products: used in the 3 months preceding the first blood draw and up to the last blood draw
  - Immunosuppressive therapy such as anti-cancer chemotherapy or radiation therapy: used in the 6 months preceding the trial vaccination and the 4 weeks following the trial vaccination
- Category 3: Oral or injectable antibiotics, which may interfere with bioassays used for antibody testing when taken before a blood draw
  - The period of collection should be within 3 days before the first blood draw and up to the last scheduled blood draw.

*Note: Inhaled and topical antibiotics (drops, creams or ointments) should not be captured.*

The information reported in the CRF for each reported medication will be limited to:

- Trade name / International non-proprietary name
- Given as treatment or as prophylaxis
- Medication category
- Start and stop dates

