### 9.3.2.2 Safety Endpoints

The observational endpoints for the evaluation of safety are:

- Occurrence, nature (Medical Dictionary for Regulatory Activities [MedDRA] preferred term), duration, intensity, and relationship to vaccination(s) of any unsolicited systemic AEs reported in the 30 minutes after vaccination(s).
- Occurrence, time to onset, number of days of occurrence, intensity, action taken, and whether the reaction led to early termination from the study, of solicited (prelisted in the subject's diary card and CRF) injection site reactions occurring up to 7 days after vaccination(s).
- Occurrence, time to onset, number of days of occurrence, intensity, action taken, and whether the reaction led to early termination from the study, of solicited (prelisted in the subject's diary card and CRF) systemic reactions occurring up to 7 days after vaccination(s).
- Occurrence, nature (MedDRA preferred term), time to onset, duration, intensity, action taken, relationship to vaccination (for systemic AEs only), and whether the event led to early termination from the study, of unsolicited AEs up to Visit 2 after vaccination(s).
- Occurrence, nature (MedDRA preferred term), time to onset, duration, seriousness criteria, relationship to vaccination, outcome, and whether the SAE led to early termination from the study, of SAEs throughout the trial.

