**9.3.2.3.3 Unsolicited Non-serious Adverse Events From Day 0 to Day 30 After Vaccination**

In addition to recording solicited reactions, parents / guardians will be instructed to record any other medical events that may occur during the 30-day period after vaccination. Space will be provided in the diary card for this purpose.

For each unsolicited non-serious AE, the following information is to be recorded:

- Start and stop datesa
- Intensity of the event:
  - For measurable unsolicited non-serious AEs that are part of the list of solicited reactions, the size of the AE as well as the temperature for fever will be collected and analyzed based on the corresponding scale used for solicited reactions (see [Table 9.1](#) and [Table 9.2](#))
  - Other unsolicited non-serious AEs will be classified according to the following intensity scale:
    - Grade 1: No interference with activity
    - Grade 2: Some interference with activity
    - Grade 3: Significant; prevents daily activity
- Action taken for each AE, if any (e.g., medication)

The action taken by the subject / guardian to treat any **unsolicited AEs** will be classified in the CRF using the following scale:

0: None

1: Medication (self-medication with an existing prescription or over-the-counter medication)

2: Health care provider contact (no new medication prescribed)

---

a The stop date of all related AEs will be actively solicited. For other events, the investigator will provide the stop date when it becomes available. AEs for which no stop date was obtained during the course of the trial will be considered as ongoing at the end of the trial.

3: Health care provider contact and prescription of a new medication (health care provider instructed subject to take a new medication, either an over-the-counter medication or one requiring a written prescription)

- Whether the AE led to discontinuation
- Whether the AE was related to vaccination (for unsolicited systemic AEs)

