#### 9.3.2.3.4 Serious Adverse Events

Information on SAEs will be collected and assessed throughout the trial, from inclusion until 30 days after vaccination.

Any SAE occurring at any time during the trial will be reported by the Investigator through the EDC system and according to the completion guidelines provided by the Sponsor. All information concerning the SAE is to be reported, either as part of the initial reporting or during follow-up reporting if relevant information became available later (e.g., outcome, medical history, results of investigations, copy of hospitalization reports). The Investigator will assess the causal relationship between the SAE and the investigational product as either “Not related” or “Related”, as described in [Section 10.4](#).

In case a subject experiences convulsion / seizure episode associated or not with fever, the assessment will be performed according to the “Guideline for definition and collection of cases of febrile convulsion” [\(48\)](#) and this event will be considered an SAE.

See [Section 10](#) for further details on SAE reporting.

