## 12.3 Handling of Missing Data and Outliers

### 12.3.1 Safety

No replacement will be done. Missing safety data will not be replaced. All subjects with safety data and all safety data recorded in the CRFs will be included in the safety analyses. No search for outliers will be performed during the statistical analysis.

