##### *Safety*

For this trial, the safety data will be assessed by applying descriptive statistical methods, supplemented by the calculation of CIs to aid interpretation. The exact binomial distribution (Clopper-Pearson method) for proportions will be used in the calculation of the 95% CIs of events. Analysis tables and listings will contain at least the descriptions listed in Table 5.2

Table 5.2: Statistical analyses for safety observational objectives

Safety Events	Time and Group	Description
Immediate unsolicited systemic AE	Within 30 minutes after injection for all subjects in Groups 1 to 12 at D0	Proportion of subjects that have the event, MedDRA terms, intensity, relationship to vaccine, study discontinuation
Solicited injection site reactions	Up to 7 days after D0 for all subjects in Groups 1 to 12	Proportion of subjects that have the event, onset, duration, intensity, action taken, study discontinuation, temperature collection routes
Solicited systemic reactions	Up to 7 days after D0 for all subjects in Groups 1 to 12	Proportion of subjects that have the event, onset, duration, intensity, action taken, study discontinuation
Unsolicited AE	Up to 30 days after D0 for all subjects in Groups 1 to 12	Proportion of subjects that have the event, MedDRA terms, onset, duration, intensity, relationship, action taken, study discontinuation
SAE	From Visit 1 to Visit 2 for all subjects in Groups 1 to 12	Proportion of subjects that have the event, MedDRA terms, onset, duration, relationship, seriousness criteria, outcome, study discontinuation

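### The SAP tabulates non-serious unsolicited AEs only to D30 although the protocol endpoint runs to Visit 2 (D30 to D44), and two SAP rules disagree on when AE onset is missing

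*SAP*

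**What the plan says.** **Window in the protocol.** The unsolicited AE endpoint in protocol 9.3.2.2 ends with "and whether the event led to early termination from the study, of unsolicited AEs up to Visit 2 after vaccination(s"). Visit 2 is 30 to 44 days after D0 (protocol 5.1.1). Collection to Visit 2 is repeated in protocol 5.1.1 and 5.1.3, in the Tables of Study Procedures, and in SAP 3.1 and 3.2. Protocol 9.3.2.3.3 instead carries a D0-to-D30 heading and tells parents to record "any other medical events that may occur during the 30-day period after vaccination". Protocol 6.7 has reportable medications collected "to the end of the solicited and unsolicited follow-up period (e.g., 30 day safety follow-up"). SAEs show the same split. Protocol 9.3.2.3.4 states: "Information on SAEs will be collected and assessed throughout the trial, from inclusion until 30 days after vaccination". Protocol 5.1.1 takes SAE collection through Visit 2.

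**Window in the SAP.** SAP 4.3 refers to protocol 9.3 for the observational endpoints. SAP 4.4.1.2.4 then limits the tables to onset from D0 to D30 or missing; an AE "with a time of onset higher than defined above will not be included in analysis, but will be listed separately". Table 5.2 gives the unsolicited AE period as "Up to 30 days after D0 for all subjects in Groups 1 to 12". Protocol 12.3.1 states: "All subjects with safety data and all safety data recorded in the CRFs will be included in the safety analyses". The matching SAP section (5.3.1) does not repeat that sentence, and SAP 5.7 does not record the D30 limit as a change.

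**Missing onset.** SAP 4.4.1.2.4 computes onset as AE start date minus vaccination date and makes it missing only when one of those two dates is missing or incomplete. SAP 5.3.1.5 makes it missing when the start date or the stop date is, and keeps such AEs in the analyses according to visit. The protocol foresees absent stop dates, in the footnote to 9.3.2.3.3: "AEs for which no stop date was obtained during the course of the trial will be considered as ongoing".

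**The concern.** The planned summary does not cover the period that the endpoint names. A non-serious AE starting on D31 to D44 is listed but gets no group percentage or confidence interval unless a further table is added.

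This may also affect the Russian Visit 2 laboratory and neurology findings, which become AEs when clinically significant. Visit 2 cannot fall before D30, so a non-serious finding dated to that visit is tabulated only if the visit is on D30 itself, one of 15 permitted days. The documents do not say which start date such a finding receives.

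The onset conflict is a separate matter. Under SAP 5.3.1.5, whether a late AE enters the 30-day table depends on whether it has a stop date, which has no bearing on when it began. Two programmers following different sections would produce different tables.

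**Working it through.** The plan gives no figure to reproduce here. The check is day arithmetic plus the application of each onset rule to example AEs.

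**Days outside the tables.** Inputs: Visit 2 on day v, with v from 30 to 30 + 14 = 44 (protocol 5.1.1); table limit D30 (SAP 4.4.1.2.4). Collection days D0 to Dv number v + 1, and those after D30 number v − 30, so the untabulated share is (v − 30)/(v + 1).

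| Visit 2 | Days after D30 | Collection days | Share |
|---|---|---|---|
| D30 | 0 | 31 | 0% |
| D33 | 3 | 34 | 8.8% |
| D37 | 7 | 38 | 18.4% |
| D44 | 14 | 45 | 31.1% |

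If Visit 2 were spread evenly over D30 to D44 (an assumption; the documents give no distribution), the total would be 105 days after D30 out of 570 collection days, or 18.4%, a mean of 105/15 = 7 days per child.

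**The two onset rules.** SAP 4.4.1.2.4 places AEs with missing onset in the 30-day table by treating them as occurring just after the vaccination that the visit number indicates. There is only one vaccination visit. The examples assume that the visit number points to it.

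| AE | Onset by 4.4.1.2.4 | Result | Onset by 5.3.1.5 | Result |
|---|---|---|---|---|
| Start D35, stop D40 | 35 | listed only | 35 | listed only |
| Start D35, no stop date | 35 | listed only | missing | in 30-day table |
| Start D10, no stop date | 10 | in table | missing | in table, onset day lost |
| Start 2 days before vaccination, no stop date | −2 | listed only | missing | in 30-day table |
| Start date missing | missing | in table | missing | in table |

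Inclusion differs for AEs with no stop date that start before D0 or after D30. For those starting within D0 to D30 inclusion agrees, but 5.3.1.5 discards a known onset day although time to onset is part of the endpoint. Stop dates are not imputed (SAP 5.3.1.5), so the situation is not resolved later.

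**The case against.** The 30-day window was not invented by the SAP. It is in the heading and diary instruction of protocol 9.3.2.3.3 and is echoed in 6.7, and the SAP's reference to protocol 9.3 takes in both windows. This is correct, and it means that the root defect is an unreconciled protocol. It does not settle which window governs the stated endpoint.

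A fixed window is also a sound choice. Visit 2 varies by 14 days, so a D0-to-Visit-2 percentage mixes children with 30 to 44 days of follow-up. That is a good reason to keep the 30-day table.

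Protocol 12.3.1 deals with missing data and outliers and can be read as a rule against dropping incomplete or extreme values. That weakens the argument from it, although its literal wording covers all recorded safety data.

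The practical effect is bounded. Late AEs are listed. Table 5.2 sets minimum content only. SAEs are also tabulated for the whole study (SAP 4.4.1.3.2), so the SAE wording conflict does not change the SAE tables. The disposition table counts terminations for AEs without an onset window (SAP 4.4.1.4.6). No hypotheses are tested. All of this stands.

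None of it answers the conflict over missing onset. SAP 4.4.1.2.4 is the dedicated derivation and its rule is exclusive, which suggests that 5.3.1.5 is the slip, but as written both apply.

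**Conclusion.** Both parts hold, and they should be fixed.

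- **Onset rules.** They contradict each other whichever window is adopted. The number of AEs affected, those with no stop date and a start outside D0 to D30, is unknown.
- **Window.** The tables leave out 0 to 14 collection days per child, at most 14 of 45 (31.1%). This rests only on the stated visit window. The documents give neither a distribution of Visit 2 dates nor an AE rate, so no change in AE percentages can be derived.

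The consequence is limited to the descriptive tables of non-serious unsolicited AEs: their stated period, their completeness and whether they can be reproduced.

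**What to change.** 1. In SAP 5.3.1.5, remove the reference to the stop date, so that onset is missing only when the AE start date or the vaccination date is missing or incomplete. This is a one-line change.
2. Keep the 30-day table and add a D0-to-Visit-2 summary of unsolicited AEs, using the two-period structure that SAP 4.4.1.3.2 already has for SAEs. State which start date a Russian Visit 2 finding receives: the added table captures findings dated up to Visit 2, but might miss one dated when results return later.
3. Reconcile protocol 6.7, 9.3.2.2, 9.3.2.3.3 and 9.3.2.3.4 with SAP 4.4.1.2.4 and Table 5.2, and record the outcome in SAP 5.7. If the sponsor settles on 30 days as the endpoint window, the endpoint and collection text must be aligned to it. The added summary then becomes supportive rather than necessary.

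The cost is one SAP correction, one protocol clarification and one extra summary, with no new data. Follow-up in the added table differs between children (30 to 44 days), so it must be read beside the 30-day table.
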